Because CSP01 non-invasive and does not achieve its primary intended purpose through chemical action within or on the body, and is not dependent upon being metabolized for the achievement of its primary intended purposes, it meets the definition of a medical device. CSP01 is a non-significant risk device in the US, because it does not meet the definition of a significant risk device under § 812.3(m) of the investigational device exemptions regulation (21CFR812)

- c. TSE/BSE risk from gelatin capsules found to be broadly acceptable as the Scientific Steering Committee (SSC) of the European Union (EU) in 2003 stated that the risk associated with bovine bone gelatin is very low or zero.^{14,15} In 2006, the European Food Safety Authority (EFSA) stated that the SSC opinion was confirmed, that the BSE risk of bone-derived gelatin was very small, and removed support for the 2003 request of excluding the skull and vertebrae of bovine origin older than 12 months from the material used in gelatin manufacturing.¹⁶

VIII. Potential benefits

1. It is hypothesized that it may be of benefit in patients with chronic idiopathic constipation. Potential benefits may include improved colonic transit, a decrease in self-reported abdominal discomfort, straining, bloating, and constipation severity, as well as improved quality of life and symptom severity.

IX. Monitoring and Quality Assurance

1. Good clinical practice
The investigator will ensure that this study is conducted in accordance with the principles of “Good Clinical Practice”, as outlined in Title 21 of Code of Federal Regulations (CFR), Part 312, subpart D, “Responsibilities of Sponsors and Investigators”; 21 CFR,

part 50, “Protection of Human Subjects”; 21 CFR, part 54, “Financial Disclosure by Clinical Investigators”; 21 CFR, part 56, “Institutional Review Boards”; and 21 CFR, Part 11, “Electronic Records, Electronic Signature”, are adhered to.

2. Institutional review board (IRB) approval

The protocol and any accompanying material to be provided to the patient (such as advertisements, patient information sheets, or descriptions of the study used to obtain informed consent) will be submitted by the investigator to the MGH IRB. Approval from the IRB must be obtained before starting the study and should be documented in a letter to the investigator specifying the protocol number, protocol version, protocol date, documents reviewed, and date on which the committee met and granted approval. Any modifications made to the protocol after receipt of IRB approval must also be submitted to the IRB for approval before implementation.

3. Informed consent

Written informed consent, in accordance with 21 CFR Part 50, must be obtained prior to participation in the study. Within the context of the inclusion criteria, a proportion of eligible patients may be exhibiting significant cognitive impairment and the lack of capacity to provide consent. As such, all patients will require surrogate consent by a legally authorized representative. The investigator or staff will determine the appropriate family member-person to contact regarding the study, based on the standard operating procedures of MGH and local and state laws. The signed consent form must remain in the patient’s medical chart and must be available for verification at any time.

4. Liability and insurance

The civil liability of the investigator, the persons instructed by the investigator and the hospital, practice, or institute in which they are employed, and the liability of the financial loss due to personal injury and other damage which may arise as a result of the carrying out of this study are governed by the terms and conditions set forth in the Clinical Trial Agreement and applicable law.

5. Documentation of study findings

Required information will be entered into the appropriate CRFs. All CRFs are to be completed accurately and promptly, and should be updated as needed so they reflect the latest information on the patient’s file. All records are to be kept in conformance with applicable guidelines and SOPs. When the study is completed, the investigator must retain the essential documents for as long as needed to comply with regulatory authority, local regulations and sponsor requirements further detailed in Section 10.2.5. The investigator shall notify the sponsor prior to moving or destroying any of the study documents.

6. Study monitoring

- a. For Investigator-Initiated Research Studies, Investigators are responsible for ensuring proper monitoring of the investigation. The Investigator’s assigned clinical monitors are responsible for inspecting the CRFs throughout the study to verify adherence to the protocol; completeness, accuracy, and consistency of data; and adherence to GCPs. The monitors should have access to patient medical records and other study-related records needed to verify entries on the CRFs. In accordance to ICH Good Clinical Practice (ICH/GCP) guidelines, the Investigator’s assigned clinical monitors must have direct access to the

investigator's source documentation in order to verify the data recorded in the CRFs for consistency.

- b. The monitor is responsible for routine review of the eCRFs at regular interval throughout the study to verify adherence to the protocol and the completeness, consistency, and accuracy of the data being entered on them. The monitor should have access to any patient records needed to verify the entries on the CRFs. The investigator agrees to cooperate with the monitor to ensure that any problems detected in the course of these monitoring visits are resolved.

The Sponsor may monitor Investigators' compliance and adherence to their contractual obligations related to disclosure of the Investigator's findings, agreed upon milestones, and safety information reporting.

7. Access to Information for Auditing or Inspections

Representatives of regulatory authorities, IRB, or of the Sponsor may conduct inspections or audits of this clinical study. If the investigator is notified of an inspection by a regulatory authority the investigator agrees to notify the Sponsor immediately. The investigator agrees to provide to representatives of a regulatory agency, IRB or IEC, or Sponsor access to source documents/records, facilities, and personnel for the effective conduct of any inspection or audit.

8. Data quality assurance

Data will be entered into a secure and validated database using eCRFs. Data entered may be checked at the point of entry and through external validation checks for accuracy. After resolution of any discrepancies and automated data-review procedures, the final data sets will be subject to a quality assurance audit. When the database is declared to be complete and accurate, it will be locked. Any changes to the database after that time can only be made by written notice. The investigator will be responsible for ensuring the accuracy, completeness, and timeliness of the data reported to the sponsor in the CRFs and in all required reports. Data reported on the CRFs, which are derived from source documents, should be consistent with source documents or the discrepancies should be explained. To ensure the quality of the clinical data across all participants and sites, a clinical data management review will be performed on all patient data. During this review, patient data will be checked for consistency, omissions, and any apparent discrepancies. In addition, the data will be reviewed for adherence to protocol and GCPs. To resolve any questions arising from the clinical data-review process, data queries will be sent for the site to complete. The principal investigator will electronically sign and date the indicated places on the CRF. This signature will indicate that the principal investigator inspected or reviewed the data on the CRF and the data queries, and that the investigator agreed with the content.

9. Study Files and Retention of Records

- a. The investigator must maintain adequate and accurate records to fully document the conduct of the study and to ensure that study data is subsequently verified. These documents should be classified into two separate categories: (1) investigator's study file, and (2) patient clinical source documents. The investigator's study file will contain the protocol/amendments, printed (or electronically archived) copies of the patient CRFs, IRB, and governmental approval with correspondence, informed consent, drug accountability

(receipt/dispensing) records, staff curriculum vitae and authorization forms, information regarding monitoring activities, sponsor/investigator correspondence, and other appropriate documents and correspondence.

- b. Patient clinical source documents for this study would include, but are not limited to, the following:
 - i. Patient identification (name, date of birth, gender)
 - ii. Documentation that patient meets eligibility criteria, i.e., relevant medical history, physical examination, and confirmation of diagnosis
 - iii. Dated notes of the day of entry into the study including study number, patient identification number, verification that the trial was discussed and written informed consent was obtained
 - iv. Dated notes for each protocol assessment and documentation that protocol specific procedures were performed
 - v. Study drug accountability (investigator must keep blinded records of volume of study drug given and timing of each daily dose based on the hospital chart; this will not entail review of the unblinded pharmacy records for the sake of maintaining the blind)
 - vi. Documentation of all adverse events, including any action taken with regard to study drug and outcome
 - vii. Concomitant medications (including start and end date, dose if relevant)
 - viii. Date of trial completion and reason for early discontinuation, if applicable

10. Confidentiality

- a. The investigator must ensure that all participants' confidentiality will be strictly maintained and that their identities are protected from unauthorized parties. Only patient initials, date of birth, and an identification code (i.e., not names) should be recorded on any form or biological sample submitted to the sponsor, IRB, or laboratory. The investigator must keep a screening log showing codes, names and addresses for all patients screened and for all patients enrolled in the trial. On CRFs or other documents that are submitted to the sponsor, participants should be identified by an identification code and not by their names.
- b. The investigator agrees that all information received from the Sponsor, including but not limited to the Investigator Brochure, the investigational product, and any other study information, remain the sole and exclusive property of the Sponsor during the conduct of the study and thereafter. This information is not to be disclosed to any third party (except employees or agents directly involved in the conduct of the study or as required by law) without prior written consent from the Sponsor. The investigator further agrees to take all reasonable precautions to prevent the disclosure by any employee or agent of the study site to any third party or otherwise into the public domain.

11. Publication

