A randomized, single center, double-blind, parallel-group, placebo-controlled study assessing the effect of CSP01 on chronic idiopathic constipation and irritable bowel syndrome with constipation

Principal/Overall Investigator:
[name], MPH

Funding:
Gelesis Inc.

Version Date:
October 30th, 2017

I. Background and Significance

a.) Historical background

Constipation remains one of the most common clinical conditions encountered by physicians with an estimated general population prevalence ranging from 2% to 28%¹ generating 2.5 million physician visits per year with an annual direct medical cost of more than \$230 million in the U.S. alone.² Constipation is a symptom described as infrequent stool passage often associated with straining or the sensation of incomplete evacuation.³ In addition to gastroenterological pathology such as poor bowel motility or outlet obstruction, there are many other etiologies of constipation such as secondary to a medical condition or medication. Chronic constipation without a demonstrable physiologic abnormality is classified by Rome III Criteria as chronic idiopathic constipation (CIC), a functional gastrointestinal disorder that exists on a spectrum with irritable bowel syndrome with constipation (IBS-C).⁴ The prevalence of CIC worldwide is 14%, and it is more common in women, elderly people, and those of lower socioeconomic status. Additionally, patients with chronic constipation report impaired quality of life comparable to other chronic conditions, and consequently tend to contribute considerably to physician visits and other healthcare costs.⁵ Therefore, there is a need for more effective and well-tolerated devices, as 50% of patients with constipation are not satisfied with available therapies.⁶

b.) Previous studies supporting the proposed research

Although CIC and IBS-C are common problems, the treatment of constipation symptoms is often provider-specific, and there is weak evidence to support many of the drugs that are commonly used in the treatment of this disorder.⁷ Lifestyle measures such as hydration, exercise, and increased fiber intake are an important component of the multi-faceted approach to treating chronic constipation prior to initiation of medical therapy.⁸ Notably, fiber supplementation significantly alleviates symptoms in patients without slow transit constipation⁹, the majority of patients with constipation.³

CSP01 is a non-systemic, orally administered capsule that contains thousands of

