Given the in vitro performance of this novel, fiber-like hydrogel, it is therefore hypothesized that the device may be of benefit in patients with CIC and IBS-C, however, analysis of how it affects whole gut motility has not been conducted. This will be observed using wireless motility capsule (WMC) testing, a non-invasive diagnostic tool capable of measuring intraluminal pressure and pH through the whole GI tract, assessing both transit and contractility. WMC has been demonstrated as a safe, convenient, and reliable method of assessing whole gut transit after a dietary intervention in a more physiologic setting than traditional manometry or scintigraphy.

II. Specific Aims

This is a single center, randomized, double-blind, parallel-group, placebo-controlled pilot study. The purpose of the study is to evaluate the efficacy of the hydrogel capsule CSP01 vs active control (carboxymethylcellulose) vs placebo in accelerating colonic motility among patients with chronic idiopathic constipation. Patients who meet the Rome IV criteria for CIC or IBS-C and who meet the inclusion criteria will be offered participation in this study.

III. Subject Selection

This study aims to recruit 53 total subjects to be enrolled at one site, Massachusetts General Hospital. The 53 subjects that this study aims to recruit factors in a dropout rate of 15%, with a final sample size of 45 subjects.

INCLUSION/EXCLUSION CRITERIA:

Inclusion

1. Age 22-70 years old
2. BMI >18.5 and <35 kg/m²
3. Rome IV criteria for functional constipation or IBS-C
4. Continued IBS-C or CIC throughout Run-in period
5. Compliant with reporting during Run-in (confirm the presence of constipation during the 7-day Run-in baseline period; patients are required to report an average of <3 continuous spontaneous bowel movements [CSBMs] and ≤6 spontaneous bowel movements [SBMs] per week via the interactive web response system).

6. Ability to follow verbal and written instructions
7. Ability to record daily bowel habits, including frequency, stool consistency (BSFS), straining (EoPS), completeness of evacuation, and Patient Reported Outcomes (PROs) (abdominal discomfort, severity of constipation, bloating, overall relief)
8. Informed consent form signed by the subjects

Exclusion

1. History of loose stools
2. History of irritable bowel syndrome with diarrhea (IBS-D) or mixed irritable bowel syndrome (IBS-M)
3. Non-compliance with reporting during Run-in

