In addition to patients of MGH, subjects from the general greater Boston population will also be recruited. Subjects from the general population will be recruited through online advertisements run using the Galen Recruitment Service. Through this service, respondents will be filtered by qualifying questions. Contact information for qualified respondents will be provided to research study staff.

IV. Subject Enrollment

a.) Methods of enrollment

1. Patients may be approached by a research coordinator in the Neurointestinal Health clinic if they have a history of chronic constipation and agree to hear more about the trial
2. Patients may be called by the research coordinator prior to their appointment and asked if they would like to hear more about the trial
3. Any patients agreeing to hear more about the trial will learn more before beginning the informed consent process should they agree to participate as well as determining whether they meet all of the inclusion criteria
4. Patients may be contacted about the research study by their MGH physician on behalf of the research team. Afterward, patients may then be contacted by the research team directly.
5. Subjects who have provided their contact information through internet advertising may be contacted by the research team directly.

b.) Procedures for obtaining informed consent

1. Patients agreeing to participate will sign an informed consent with the study doctor at the time of enrollment, after proper informed consent has been provided by the site.

c.) Treatment assignment and randomization

1. Patients who have been enrolled and consented in the trial will be randomized with a ratio of 1:1:1 with 15 subjects per arm: 15 subjects on 3 capsules BID of CSP01, 15 subjects on 3 capsules BID (morning, evening) of carboxymethylcellulose (CMC), and 15 subjects on 3 capsules BID of placebo (sucrose).
2. We will stratify by Rome IV diagnosis of CIC vs. IBS-C to avoid clustering of IBS-C patients in one group.
3. The study personnel and patients will be blinded to treatment allocation.
4. Patients who fulfill study admission criteria and have a signed consent form will be assigned a 3-digit sequential patient number. The number will be used throughout the study.

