2. Specific data to be collected through patient-reported questionnaires
 - a. Spontaneous Bowel Movement (SBM) frequency rate
 - b. Complete Spontaneous Bowel Movement (CSBM) frequency rate
 - c. Stool consistency (Bristol Stool Form Scale)
 - d. Straining (Ease-of-Passage Scale)
 - e. Abdominal discomfort (Self Assessment on 0–10-point numerical rating scale)
 - f. Bloating (Self Assessment on 0–10-point numerical rating scale)
 - g. Constipation severity (Self Assessment on 0–10-point numerical rating scale)
 - h. Overall relief (Self Assessment on 0–10-point numerical rating scale)
 - i. Balloon Expulsion Time (BET) before and after
 - j. Constipation symptom severity (PAC-SYM)
 - k. Constipation quality of life (PAC-QOL)
 - l. Need for rescue laxatives
3. Study endpoints – As above
4. Statistical methods
 - a. Analysis populations
 - i. Intent-to-treat (ITT) population: all patients who are randomized will be included in the ITT population. This will be the primary population for all analyses of demographics, patient characteristics and disposition, and efficacy data.
 - ii. Safety population: All patients who are randomized and receive any study treatment will be included in the safety population. This will be the primary population for all analyses of safety data
 - iii. Per-Protocol (PP) population: All patients who are randomized and receive the study medication on each day of their hospitalization. Major protocol violations include the following:
 1. Prohibited concomitant medication usage (specifically standing laxatives during hospitalization)The PP population may be used for supplementary analysis of selected efficacy and safety data, as appropriate.
 - b. Endpoint analyses
 - i. Primary endpoint: Colonic transit times will be compared in a paired fashion for individual patients before and after the intervention by means of a repeated measures ANOVA using a 3x2 design to distinguish between the outcomes of the three different groups. We will also use multivariable linear regression to compare change in transit time after adjusting for confounders, specifically: presence of IBS-C, abnormal balloon expulsion testing indicating dyssynergic defecation ($BET \geq 2$ minutes), age, and sex.

ii. Secondary endpoints: The secondary endpoints will be compared in a similar fashion, with logistic regression adjusting for confounders.

c. Power analysis

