This is a randomized, double-blind, single-center clinical exploratory pilot comparing treatment with CSP01 to standard control (CMC) to placebo (sucrose) for prevention of constipation in patients with chronic idiopathic constipation. Notably, there is no data either from the wireless motility capsule or from radio-opaque marker transit studies establishing a clinically-meaningful threshold for change in transit time in response to any colonic motility agent, and our hope is that transit data combined with patient-reported outcomes (our secondary endpoints) from this pilot study would provide a meaningful transit improvement threshold that may be used in future research as well. There is some data demonstrating the effect of dietary fiber on colonic transit time.⁷ If we extrapolate data from the trial of dietary fiber on colonic transit time, which demonstrated a 10-hour difference in colonic transit time with a standard deviation of 12 hours, we would assume the same effect for our standard fiber (CMC) group. Assuming that CSP01 would give an additional 3-hour decrease in colonic transit over conventional fiber, our current sample size would have 94% (with $\geq 90\%$ considered excellent) power to detect a difference. Even with 30 total subjects, we would still have 80% power (see graph below which varies the sample size).

Power Analysis/Sample Size Determination.
For a Repeated Measures Anova with Indicated Specifications, & Assuming
A Test-Retest Correlation of 0.7

If we are more conservative with the effect of CSP01 over standard fiber and decrease the additional effect to 1 hour decreased colonic transit time (1/3 of what

we would expect), we would still have 88% power with our current sample size.

VII. Risks and discomforts

1. Device side effects and adverse events

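### Randomization is stratified by CIC versus IBS-C, but the powered primary ANOVA omits the stratum and no model is named as decisive; the population wording also needs aligning

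*Combined protocol and SAP*

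**What the plan says.** On the population, the protocol speaks in two ways.

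- CIC only: the aim in Section II ("in accelerating colonic motility among patients with chronic idiopathic constipation"), the power section VI.4.c ("for prevention of constipation in patients with chronic idiopathic constipation") and the benefit statement in Section VIII.
- CIC and IBS-C: the title ("assessing the effect of CSP01 on chronic idiopathic constipation and irritable bowel syndrome with constipation"), the rationale in I.c ("hypothesized that the device may be of benefit in patients with CIC and IBS-C"), inclusion criteria 3 and 4, and the sentence directly after the aim ("Patients who meet the Rome IV criteria for CIC or IBS-C and who meet the inclusion criteria will be offered participation in this study").

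On randomization, Section IV.c, item 2 says: "We will stratify by Rome IV diagnosis of CIC vs. IBS-C to avoid clustering of IBS-C patients in one group".

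On analysis, VI.4.b.i compares colonic transit times "by means of a repeated measures ANOVA using a 3x2 design to distinguish between the outcomes of the three different groups". That design has three groups and two times, with no diagnosis term. The same item then adds a multivariable linear regression of change in transit time, adjusted for IBS-C, abnormal balloon expulsion, age and sex. It does not rank the two analyses. Neither contains a treatment-by-diagnosis term, and no estimate by diagnosis is planned. No expected IBS-C share is given.

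**The concern.** A factor important enough to stratify on normally belongs in the primary test. Stratifying makes the arms more alike than chance would. An analysis that ignores the stratum leaves any diagnosis-related variation in the error term, so it takes no credit for that balance. If diagnosis predicts the change in transit, the standard error is overstated, the test rejects too rarely and power is lost.

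With two models and no ranking, the primary p-value could also come from either. And because the aim names CIC while the sample is mixed, a pooled result could be reported under a label that does not match who was enrolled.

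**Working it through.** **Inputs from the plan.** IV.c, item 1: "randomized with a ratio of 1:1:1 with 15 subjects per arm". From VI.4.c: SD 12 h, CMC effect 10 h, a further 3 h for CSP01 (1 h in the cautious case), and pre/post correlation 0.7.

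**Assumed.** Alpha is 0.05 (not in the readable text). The IBS-C share is 40%, taken as 6 of 15 in every arm. The two diagnoses differ in mean CTT change by D = 0, 3, 6 or 10 h.

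**1. Reproduce the stated power.** With two time points, the group-by-time test is a one-way ANOVA on change.
- SD of change = 12 × √(2 × (1 − 0.7)) = 9.30 h; variance 86.4.
- Changes of 0, 10 and 13 h have mean 7.67 and squared deviations summing to 92.67. So λ = 15 × 92.67 / 86.4 = 16.09. On 2 and 42 df the power is 94.3% (stated 94%).
- With 10 per arm it is 79.8% (stated 80%). With 0, 10 and 11 h, λ = 15 × 74 / 86.4 = 12.85 and power is 88.2% (stated 88%).

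All three figures reproduce, so the powered test is the group-by-time test without the stratum.

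**2. When the omission matters.** A constant difference in transit level between CIC and IBS-C cancels in each patient's change. Only a difference D in mean change matters.

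**3. Size.** Ignoring the stratum adds 15 × 0.4 × 0.6 × D² = 3.6 D² to the error sum of squares in each arm. Over three arms that is 10.8 D², and on 42 df the error variance becomes 86.4 + 0.257 D². Because the strata are balanced, the true variance of an arm difference stays at 86.4 × 2/15. The 95% half-width for a pairwise difference is 2.018 × SD × √(2/15). Type I error and power at 0/10/13 h come from simulation; ranges show the spread between repeated runs.

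| D (h) | Error SD (h) | Half-width (h) | Type I error | Power, no stratum | Power, with stratum |
|---|---|---|---|---|---|
| 0 | 9.30 | 6.85 | 5% | 94% | 94% |
| 3 | 9.42 | 6.94 | 4.4–4.6% | 94% | 94% |
| 6 | 9.78 | 7.21 | 3.6–3.7% | 92–93% | 94% |
| 10 | 10.59 | 7.80 | 2.0–2.2% | 89% | 94% |

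With the stratum in the model (41 error df), the half-width is 6.85 h whatever D is. For IBS-C shares from 20% to 50%, omitting the stratum widens the interval by about 1% at D = 3 h, 3–5% at 6 h and 9–14% at 10 h. Power is then about 94%, 92–93% and 87–90%.

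**4. Precision by diagnosis.** At a 40% share there are 9 CIC and 6 IBS-C patients per arm. The half-widths are 2.064 × 9.30 × √(2/9) = 9.0 h and 2.131 × 9.30 × √(2/6) = 11.4 h. Both are at least three times the 3 h advantage assumed for CSP01 over CMC.

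**The case against.** The strongest reply is that the remedy is nearly in the plan. With two time points, an ANOVA with diagnosis-by-time gives the same group comparison as a regression of change on group and diagnosis. VI.4.b.i already lists a regression of change that includes IBS-C. This stands in part: diagnosis is not ignored. But the regression is introduced as an addition, the power was computed for the unadjusted test, and nothing says which one decides.

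Second, the loss is hypothetical. The documents give no figure for D or for the IBS-C share, and a 10 h difference is as large as the whole assumed CMC effect. If the planned 12 h SD already describes a mixed sample, the stated 94% already absorbs the loss. Adjustment would then be a gain, to about 96% at D = 6 h. This stands as a limit on size. It does not argue for leaving the stratum out.

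Third, the CIC-only text may be loose drafting. That is the likelier reading. A reader might infer that the trial estimates an effect in a different population from the one intended. The documents do not support this: the title, hypothesis, eligibility and stratification all make the mixed population the evident target. A pooled effect departs from the CIC effect only if the treatment effect differs by diagnosis, and the plan gives no figure for that. Adding the stratum as a main effect would not turn the result into a CIC-only estimate either.

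**Conclusion.** The point holds and is modest. The powered primary test leaves out the randomization stratum, the adjusted model is not ranked against it, and three sections name a narrower population than the one enrolled.

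A reader might infer that the primary intervals are too wide as a matter of course. That does not follow. The loss is nil if the diagnoses change alike, and at the assumed 40% share power falls by no more than about 2 points up to a 6 h difference. It reaches about 5 points, with type I error near 2%, only at 10 h. Any error is conservative: simulated coverage of the unadjusted interval runs from 95.2% at D = 0 to 97.6% at 10 h, so the omission would not produce a false positive claim. These sizes rest on the assumed share, D and alpha, and on 9.3 h being the SD of change within diagnosis.

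The population conflict is one of wording, but it sits in the statement of purpose and has to be settled in the text.

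**What to change.** 1. In VI.4.b.i, add diagnosis and diagnosis-by-time to the primary repeated measures ANOVA; equivalently, make a model of CTT change on treatment and randomization stratum the primary analysis. State that this model decides, and keep the regression with balloon expulsion, age and sex as supportive.
2. In Sections II, VI.4.c and VIII, name the population as CIC or IBS-C, to match the title and inclusion criterion 3.
3. Report the CTT treatment effect with 95% CI separately for CIC and IBS-C, labelled descriptive.

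The cost is one error degree of freedom (42 to 41), which leaves power at 94.3% when D = 0, plus a few sentences of text. The estimates by diagnosis will be imprecise and should not be used to claim or deny an effect in either group.
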